Specific Aim 3: Conduct a pilot randomized controlled trial of the brief, Veteran-targeted PCI in a sample of recent Veterans with stress-related mental health disorders (n=48) to assess feasibility and preliminary efficacy.

Hypothesis 3a: The brief PCI will be shown to be feasible as evidenced by successful rates of recruitment, attendance at intervention sessions by Veterans, and interventionist fidelity to the intervention.

Hypothesis 3b: Compared to a health and wellness control intervention, participation in the brief, Veteran targeted PCI will result in significant increases in (1) Veteran PCC behaviors in mental health care encounters and (2) functioning in domains of health, purpose, and community.

Secondary analysis: Comparing the RCT arms, explore (1) Veteran attrition from VA mental health care via chart review and (2) Veteran self-assessment of levels of clinical symptomology with the DASS-21, AUDIT, DAST 10, and PCL-5.

2 * Discuss the research design including but not limited to such issues as: probability of group assignment, potential for subject to be randomized to placebo group, use of control subjects, etc.:

Aim 1: 35 recent Veterans with stress-related mental health disorders and their VA mental health providers will consent to audio-recording of one treatment encounter. (There is no randomization or group assignment.)

Aim 2: Two focus groups of 4-6 Veterans each will be held. We will also conduct a clinical demonstration of the PCI with 10 Veterans to examine acceptability and further refine the intervention. Participants will complete the three session intervention and participate in a qualitative interview about their experience. (There is no randomization or group assignment.)

Aim 3: We will conduct a pilot randomized controlled trial of the PCI (n=48) to assess feasibility and preliminary efficacy. 24 participants will be randomized to a health and wellness control condition and 24 to the experimental treatment condition.

3 * Describe the relevant prior experience and gaps in current knowledge. Describe any relevant preliminary data:

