After all survey and coding data has been captured into the database, frequency tables for all variables and histograms for continuous variables will be examined. Missing data and potential errors will be investigated and resolved. Scales and subscales will be scored. Normal Q-Q plots will be examined for continuous variables to check normality, skew, and to assess whether transformations are needed to examine the associations. Descriptive statistics will be calculated on demographic variables to characterize the sample. To assess PCC behaviors, descriptive statistics will be calculated for all PCC subscales and variables from coding, including: minimum, 25th percentile, median, mean, 75th percentile, maximum, and standard deviation. The descriptive statistics will be collected and displayed in tables separately for Veterans and providers along with histograms to visually assess overall distributions and variability. For these analyses, each patient-prescriber dyad will be treated as a unique encounter. Proportions of patients and providers meeting certain levels of the 4 components of PCC will also be calculated along with 95% confidence intervals.

Aim 2 data analyses

Aim 2 Veteran focus groups and refinement of materials. Once a draft of the PCI is developed, two focus groups of 4-6 Veterans each will be held (1-1.5 hours each). The focus groups will be led by the PI and observed by the coordinator, who will also take observational notes. Participants will be asked to comment on and critique the draft PCI structure and content. Because the goal is to elicit concrete suggestions and feedback with which to develop the PCI, focus group transcripts will not be coded to identify overarching themes or quotes. Rather they will be used to identify suggestions for PCI modification. Study team members will utilize the transcripts, observational notes, and personal observations to summarize focus group discussion and suggestions from focus group participants into an organized document for the EAP. In addition, relevant study team members will present the findings and be available for questions during EAP Meeting 3.

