Aim 2 clinical demonstration of the PCI. The final task in Aim 2 will be to complete a clinical demonstration of the PCI (in its form after Meeting 3 input is incorporated) to examine acceptability using qualitative interviews. Participants will be 10 recent Veterans with current stress-related mental health diagnoses. The interventionist will be the same interventionist who will deliver the PCI in Aim 3. The

purpose of the clinical demonstration is to identify PCI features or materials that appear functional in theory but do not execute well in a clinical setting. At the end of their participation in the clinical demonstration, each Veteran will complete a qualitative semi-structured interview that will discuss their experience with the PCI and their thoughts about its overall utility. The interview will ask for feedback about the PCI content, materials, scheduling, and experience. This will include review of the format and content of the sessions, handouts, and educational materials. Questions will focus on the participants' reactions to the content, including utility and clarity. Interviews will begin with broad open questions about initial reactions, explore those thoroughly, and subsequently ask specific follow up questions to elicit information about each facet of the intervention. After each interview the interviewer will append a field note documenting pertinent observations. Interviews will be in-person and recorded for verbatim transcription to facilitate coding.

Aim 2 analysis of semi-structured interviews. We will use qualitative RAP to analyze the semi-structured interviews. RAP is ideal for PAR studies with action-oriented goals: it uses team-based coding and focuses data analysis in order to answers to specific research questions.

Aim 3 data analysis.

First, summary statistics of demographic, clinical, and baseline outcome scale scores will be calculated for the total sample and compared between treatment groups to check the success of the randomization and for outliers. If there is an out-of-balance variable that is plausibly a prognostic factor for PCI outcome, we will adjust for this variable when comparing the two treatment arms. Nesting of multiple patients within the same provider will be identified.

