Aim 3, hypothesis 3b. We hypothesize that compared to control participants, participation in the brief, Veteran-focused, PCI will result in significantly greater increase in (1) Veteran PCC behaviors in mental health care encounters as measured by the MPCC and (2) functioning in domains of health, purpose, and community as measured by the VR-36 and WHODASS. Our overall approach will be to compare group means using a mixed model, accounting for common providers among participants with a random provider effect. If

an out of balance prognostic covariate is found in baseline comparisons this variable will also be included in the model, although the number of covariates that can be adjusted for will be limited by the sample size. We chose to use mixed models versus GEE (generalized estimating equations) to avoid bias due to unequal cluster sizes or sample size.

More specifically, for hypothesis 3b(1) to compare the treatment arms on PCC behaviors in mental health care encounters we will use the MPCC, assessed only at time point 2. The independent variable will be the treatment group indicator. For hypothesis 3b(2) to examine whether relative to control the treatment group has greater functioning (subscales of the VR-36 and WHODAS), we will compare group means at time points 3 and 4 using a linear mixed model ANCOVA. The comparison at time point 3 will be primary and at time point 4,

secondary. For this hypothesis, after adjustment for baseline, there will be 2 repeated measures (time points 3 and 4) which will be assumed to be correlated (i.e. thru correlated error terms). However, contrasts will be specified in order to compare the groups at time point 3, separately from time point 4.

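### Aim 1 intervals make no allowance for Veterans who share a provider, and its provider proportions count a repeat provider more than once

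*Combined protocol and SAP*

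**What the plan says.** Under Justification, Objective, & Research Design, item 2, Aim 1 is set out as follows: "35 recent Veterans with stress-related mental health disorders and their VA mental health providers will consent to audio-recording of one treatment encounter". Each Veteran therefore gives one encounter. Nothing limits a provider to one Veteran, and the number of providers is not given.

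Under Sample Size and Data Analysis, item 2, the Aim 1 paragraph fixes the unit of analysis: "For these analyses, each patient-prescriber dyad will be treated as a unique encounter". The next sentence reads: "Proportions of patients and providers meeting certain levels of the 4 components of PCC will also be calculated along with 95% confidence intervals". The interval method is not named. The paragraph contains no clustering term and no count of encounters per provider.

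The Aim 3 paragraphs of the same item treat the same structure differently. At the baseline step, "Nesting of multiple patients within the same provider will be identified". The outcome model for hypothesis 3b compares group means while "accounting for common providers among participants with a random provider effect". Both aims code recorded encounters with the same instrument, the MPCC.

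**The concern.** Encounters with one provider share that provider's style. Thirty-five encounters from fewer than 35 providers then carry less information than 35 independent ones, and an interval computed as if they were independent is too short. Provider behaviours are the most exposed.

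A second problem does not depend on correlation. Aim 1 sets out to describe rates for providers as well as Veterans. With the dyad as the unit, a provider recorded several times enters the numerator and denominator several times, so the point estimate as well as the interval answers a question about encounters. A provider may also meet a level in one encounter and miss it in another, and the plan has no rule for that case.

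At stake is whether the Aim 1 rates are reported with honest precision and a correct label.

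**Working it through.** **Is there a figure to reproduce?** No. Aim 1 has no precision, power or sample-size calculation.

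**Inputs**
- Encounters: n = 35, one per Veteran (Research Design, item 2).
- Providers and mean encounters per provider (m): not given; assumed.
- Intraclass correlation within provider (ICC): not given; assumed.
- True proportion: p = 0.5, chosen because it gives the widest interval.
- Interval method: not given; the simple normal interval is used for the arithmetic and the Wilson interval for the simulation.

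**Step 1, independence.** Half-width = 1.96 × √(0.5 × 0.5 / 35) = 0.166, or 16.6 points. The Wilson interval at 50% runs from 34.3% to 65.7%.

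**Step 2, shared providers.** The design effect is DE = 1 + (m − 1) × ICC. The half-width needed is 16.6 × √DE. The actual coverage of the unadjusted interval is about 2Φ(1.96/√DE) − 1.

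| m (assumed) | ICC (assumed) | DE | Half-width needed | Coverage of unadjusted interval |
|---|---|---|---|---|
| 1 (all distinct) | any | 1.00 | 16.6 | 95% |
| 1.5 | 0.1 | 1 + 0.5 × 0.1 = 1.05 | 17.0 | 94% |
| 2 | 0.3 | 1 + 1 × 0.3 = 1.30 | 18.9 | 91% |

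**Step 3, simulation.** Beta-binomial data (100,000 runs, p = 0.5) give these coverages for the nominal 95% Wilson interval, which covers 96% with no clustering:

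| Providers supplying 35 encounters (assumed) | ICC 0.10 | ICC 0.30 |
|---|---|---|
| 20 | 95% | 93% |
| 12 | 94% | 89% |
| 7 | 92% | 83% |
| 5 | 89% | 77% |
| 11, uneven, largest with 8 | 92% | 83% |

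The loss is negligible to small with 20 providers. It becomes material when a handful of providers supply most encounters. An uneven split does more harm than the mean m suggests: 11 providers average 35/11 = 3.2 encounters, yet coverage resembles that of 7 equal providers.

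**Step 4, the provider proportion.** In the uneven illustration, the provider with 8 encounters carries 8/35 = 22.9% of the weight in a dyad-based proportion, against 1/11 = 9.1% if each provider counts once. This holds at any ICC.

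**The case against.** The strongest reply is that the premise is inferred. No sentence says that Aim 1 providers repeat, the interval method is unstated, and the quoted rule names a unit of analysis without mentioning shared providers. This stands in part, and the point is therefore conditional. But since each Veteran gives one encounter, a rule that each dyad counts as unique has content only if some providers recur.

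Second, the planned enrolment hints at mild clustering. Participant Selection, item 2, gives 171 in total. Subtracting the Veterans (35 + at most 12 in focus groups + 10 + 48 = 105) leaves 66 for the advisory panel and all Aim 1 and Aim 3 providers. With an assumed 15 panel members, 51 providers would share at most 35 + 48 = 83 recordings, about 1.6 each. This is suggestive only, because the 171 is not split by aim and may include over-enrolment. It does argue against leaning on the severe rows of the table.

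Third, Aim 1 is descriptive and Aim 3 makes a between-arm comparison, so a lighter treatment in Aim 1 is not in itself a contradiction. That is fair. An interval is nonetheless an inferential statement, and it should cover at its stated rate.

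Fourth, the decisions are past. The section on audio recording speaks of Aim 1 recording in the past tense, and the payment section refers to RCT participants already enrolled. The remedy is therefore one of reporting.

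A reader might also infer that narrow intervals make differences between PCC components look firmer than they are and so misdirect the intervention. The documents do not support this. The Aim 1 analysis plans no comparison between components, and any such comparison would be paired within encounters. Development also drew on barriers and facilitators, focus groups and the Expert Advisory Panel, and the move to Aim 3 rested on a 75% panel vote. No decision turns on an interval width.

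**Conclusion.** The point holds in conditional form and is modest. If at least one Aim 1 provider contributes more than one encounter and the ICC is positive, the planned 95% intervals are too narrow. If any provider repeats, a dyad-based provider proportion is mislabelled whatever the ICC.

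On the assumed mild to moderate inputs, the understatement is about 0.4 to 2.3 points on a 16.6-point half-width (17.0 − 16.6 and 18.9 − 16.6), with coverage of about 94% to 91%. Coverage in the low 80s or below might be inferred from the extreme scenarios. It requires that few providers, or a few dominant ones, supply most encounters and that the ICC is high, and the documents establish neither. If all providers are distinct, there is no error. The Aim 3 treatment comparison is not affected.

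**What to change.** Replace the dyad sentence in the Aim 1 analysis with text to this effect:

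1. Report the number of distinct Aim 1 providers and the distribution of encounters per provider.
2. If any provider appears more than once, compute intervals for the Aim 1 proportions with a method that allows for clustering by provider and includes a small-sample correction. Examples are a Wilson interval with n divided by the estimated design effect, or a cluster-robust variance with t degrees of freedom based on the number of providers. If all providers are distinct, keep the ordinary interval.
3. For provider proportions, either use one value per provider under a stated rule (for example, the provider's mean score across encounters compared with the threshold) or label the result as a proportion of encounters.

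An uncorrected cluster-robust interval can under-cover with few providers, which is where the problem is largest. A logit mixed model is a poor substitute: it estimates a conditional rather than a marginal proportion, and its random intercept is not separately identifiable when every provider appears once.

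The cost is a short re-analysis of existing recordings and somewhat wider intervals. With few providers or few repeats the design effect will itself be imprecisely estimated, and the report should say so. No new data are needed.

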The primary goal of the Aim 3 pilot RCT is to assess the feasibility of PCI for a larger confirmatory RCT. After considering time and resources available with this CDA-2, we believe it will be feasible to randomize 24 individuals per condition. We expect 20% of those randomized in each condition will miss data collection at TP3, and 30% at TP4. This sample size will not be sufficient to detect "small" clinically important differences at TP3 (post-treatment) with 80% power as would be expected of a larger confirmatory RCT. However, with the anticipated 19 participants per condition with complete data at TP3, power is estimated to be equal to .80 for detecting between "medium" and "large" effect sizes ($d=.65$) with the ANCOVA analysis, assuming TP1 to TP3 or TP4 correlation in the response variable is $r=0.7$.

2 * Provide the plan for data analysis. Include in the description the types of comparisons that are planned (e.g., comparison of means, comparison of proportions, regressions, analysis of variance, etc.), which is the primary comparison/analysis, and how the analyses proposed will relate to the primary purposes of the study:

Aim 1 data analysis.

Audio recordings of Aim 1 will not be transcribed as outlined in Aim 2. Recorded Veteran-provider encounters will be coded by research staff using the Measure of Patient-Centered Communication (MPCC). Theoretically grounded in Stewart et al.'s model of patient-centered care, the MPCC is a method for trained raters to assess and quantify recordings of patient-provider encounters. It does not necessitate that the recorded encounters be transcribed for coding. The MPCC has been used to code many types of patient/provider encounters including care for acute and chronic conditions, routine physicals, follow-up visits and emergency department encounters.

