Appointment recording coding. Similar to the procedures described in 3b11 (Aim 1 data analysis), the PI will work with two research team staff members to code recorded appointments with the MPCC. We will all code the first 4 recordings to confirm coder competence and establish interrater reliability. After the first 4 recordings coders will code recordings individually until every seventh recording. Every seventh recording I and the research team members will again all code the same recording and check for agreement. Through this process 20% of the recorded appointments will be coded and compared by multiple coders.

Aim 3, hypothesis 3a. The brief, Veteran-targeted, PCI will be shown to be feasible as evidenced by adequate rates of recruitment, Veteran attendance at PCI sessions, and interventionist fidelity to the PCI. We will track: (1) actual recruitment compared to recruitment goals; (2) number of sessions each participant attends, enabling us to identify initial engagement, overall attendance rates, and drop-out; (3) number of reminder and outreach contacts required to keep participants engaged, indicating how much staff time is required to successfully facilitate involvement; (4) interventionist adherence to the PCI; and (5) qualitative feedback from a subsample of pilot RCT intervention arm participants as described in section 3d9. Recruitment feasibility will be assessed by a proportion equal to # of patients who sign consent / # of patients approached. To account for sampling variability we will also calculate a 95% confidence interval. Attendance will be collected at each PCI session and stored in our database. We will calculate the proportion of sessions attended for each participant. Feasibility will be demonstrated if at least 80% of PCI participants attend at least 2 out of 3 of PCI sessions. Interventionist fidelity will be measured by our interventionist adherence rating scale. A random selection of 25% of the PCI session recordings will be analyzed, stratified by month over the course of the pilot RCT, to examine potential changes in the way the PCI is delivered over time. After study completion we will calculate overall percentages for each item of the scale to assess overall fidelity. Interventionist fidelity will be demonstrated if at least 90% of interventionist behaviors in the analyzed PCI sessions have been rated acceptable or excellent.

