- If meeting face-to-face with a veteran for their individual session(s) is not possible then a trained study interventionist may (1) transport a study audio recorder to capture the audio of any individual session(s) completed via telehealth visit or (2) utilize the VA's protocol for Recording in CAG using Audacity Application and will export the recording to a restricted access VA sharedrive. If the interventionist uses an audio recorder they will utilize their locked HIPAA bag to transport the recorder, to ensure its protection.

- If meeting face-to-face with a veteran for their regularly scheduled mental health care is not possible and the veteran has provided consent to record one of their regularly scheduled mental health care appointments, then the study team will approach the veteran's mental health care provider to ask if they are willing to utilize the VA's protocol for Recording in CAG using Audacity Application. If they agree then the study team will make arrangements with the clinician to receive the recording via a sharedrive and immediately export the recording to a restricted access VA sharedrive.

Behavioral Intervention

You indicated that this study involves psychosocial or behavioral interventions.

1 * Describe the intervention (duration, number of sessions, focus, etc.):

Aim 3

Treatment condition. We anticipate that the person-centered intervention (PCI) will be comprised of three, one-hour sessions offered over three to six weeks, scheduled at the participants' preference. Sessions will be one-on-one with the interventionist. The PCI sessions will be offered in a private room in the same buildings that VA mental health services are located in, on the two respective VAMHCS campuses OR will be offered via VA Video Connect, the VA's telehealth program which uses encryption to ensure a secure and private session, OR phone.

Control condition. The control condition will be an educational health and wellness intervention for stress related disorders that will match the experimental condition for time and attention. The control condition will be three, one hour, individual sessions covering the symptom cycle, managing stress, and identifying social supports. The interventionist will be a non-blinded member of the research team such as the

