PI or coordinator. The control sessions will be offered in a private room in the same buildings that VA mental health services are located in, on the two respective VAMHCS campuses OR will be offered via VA Video Connect, the VA's telehealth program which uses encryption to ensure a secure and private session, OR phone.

ID: VIEW4E0BC12A9F800
Name: v2_Behavioral Interventions

Data Collection/Record Review

You indicated on the "Type of Research" page that your study involves data collection or record review (i.e., chart review, not self-report).

1 * What type of data will be collected/analyzed in this study? (Check all that apply)

Retrospective/Secondary Analysis (data has already been collected at the time of initial IRB submission)
 Prospective (data is not yet in existence and/or collected)

2 * Will this study involve adding data to a registry or database for future use?

Yes No

3 * Will the data be released to anyone not listed as an investigator on the protocol?

Yes No

3.1 If Yes, give name(s) & affiliation(s):

ID: VIEW4E0E25A8CA400
Name: v2_Data Collection / Record Review

Prospective Data

You indicated that the study involves the collection of prospective data.

1 * Where is the data being collected from? (Check all that apply)

- Medical records
- Medical images
- Commercial (for profit) entity
- Publicly available records
- Schools
- Other

1.1 If Other, please specify:

2 * What data fields will you have access to/collect for the study? For example, name, initials, date of birth, Social Security number, income, demographic information, family units, housing, etc.

The following information will be collected from VA medical records: 1) Veteran name 2) Veteran address 3) period of military service 4) mental health/substance use diagnoses 5) initial date of mental health and/or alcohol/drug abuse treatment service use 6) last date of mental health and/or alcohol/drug abuse treatment service use.

Near the end of study participation, Veteran service use data will be collected for the period of time the Veteran was enrolled in the study. This will include number of mental health, physical health, and Whole Health appointments and appointment dates.

You can also upload a copy of the data fields/variables to be collected for the study:

Name	Created	Modified Date
------	---------	---------------

There are no items to display

ID: VIEW4E0E25B643800
Name: v2_Prospective Data

Clinical Trial Registration

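### The supplied plan lets a non-blinded PI or coordinator deliver control sessions and has the PI code the rater-scored MPCC, with no stated coder masking or separation of roles

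*Combined protocol and SAP*

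**What the plan says.** Four parts of the combined protocol and SAP bear on this.

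- **Who codes.** Sample Size and Data Analysis, Aim 3, Appointment recording coding: "the PI will work with two research team staff members to code recorded appointments with the MPCC". All three code the first four recordings and every seventh one after that. The rest are coded by one person. The plan puts the jointly coded share at 20%.
- **What the coding feeds.** For the between-arm comparison in hypothesis 3b(1), "we will use the MPCC, assessed only at time point 2". The Aim 1 analysis text describes the instrument: "the MPCC is a method for trained raters to assess and quantify recordings of patient-provider encounters".
- **Who delivers sessions.** Behavioral Intervention, Control condition: "The interventionist will be a non-blinded member of the research team such as the" (the sentence continues) "PI or coordinator. The control sessions will be offered in a private room". For the experimental arm, the Aim 2 clinical demonstration text says "The interventionist will be the same interventionist who will deliver the PCI in Aim 3".
- **Who hears recordings.** Under Audio or Video Recording, item 2, the individual sessions are recorded to train and supervise staff. Confidentiality of Data, item 2, lets the PI and other research staff view recordings for supervision.

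The nearest safeguards are recordings that carry a code and no name (Audio or Video Recording, item 4; Confidentiality of Data, item 2) and the agreement checks. The word non-blinded in the control-condition text is the only reference to blinding in the supplied documents.

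**The concern.** A person who has spent three one-hour sessions with a participant knows that participant's arm. If the same person later scores that participant's recorded appointment, the score is not blind. The MPCC comparison is exposed to this because trained raters produce the score and it is the only stated measure for 3b(1).

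The analysis has little that could absorb an arm-related shift. There is no baseline MPCC score to adjust for. The model has a random provider effect and possible prognostic covariates, but no coder term. Agreement checks measure consistency, and coders who share knowledge of the arm can agree on a shifted score.

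What is at stake is the preliminary efficacy signal on Veteran behaviour in appointments, which would help inform the larger trial that the investigator intends to propose.

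**Working it through.** **1. Roles side by side.**

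| Role | Person named | Masked to arm? |
|---|---|---|
| Control interventionist | Non-blinded team member; PI or coordinator as examples | No, by the plan's own wording |
| PCI interventionist | Same person as in the Aim 2 demonstration; not otherwise identified | Not stated |
| Viewing recordings for supervision | PI and other research staff | Not stated |
| Aim 3 MPCC coder | PI and two research staff | Not stated |

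The PI is a definite coder, a possible control interventionist and a possible viewer of session recordings. The two staff coders are not identified, so the coordinator could be one of them. No supplied sentence separates these roles or moves a coder's own participants to someone else.

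**2. The plan's 20% joint-coding figure.** Joint codings = 4 + floor((N − 4)/7), where N is the number of recordings. N is not given, because recording is optional and the provider must agree. I assume 48 (everyone randomised) and 38 (19 per arm, borrowing the plan's expected TP3 completers).

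- N = 48: 4 + floor(44/7) = 10 joint; 10/48 = 20.8%; 38 solo.
- N = 38: 4 + floor(34/7) = 8 joint; 8/38 = 21.1%; 30 solo.
- N = 38, if every seventh means recordings 7, 14, 21 and so on: 9 joint; 9/38 = 23.7%; 29 solo. N = 48 is unchanged on this reading.

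The stated 20% reproduces. Roughly 76% to 79% of recordings therefore rest on one coder's score.

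**3. Do the safeguards mask the arm?** A code in place of a name protects confidentiality. It does not stop someone who treated a participant from recognising the voice or the content. Agreement checks cover about a fifth of recordings and cannot detect a shift that all coders share.

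**4. Size.** The documents give no size for a coding shift, no division of solo coding, and no fixed control interventionist. Neither the bias nor the number of affected recordings can be calculated. As illustration only, suppose there is no true effect and arm-aware coding moves the arms apart by s standard deviations. For a two-sample t test with 19 per arm, two-sided 5% (the plan states no alpha) and provider clustering ignored, the noncentrality is s × √(19/2) with 36 degrees of freedom. The false-positive rate is then 0.06, 0.09, 0.15 and 0.32 for s = 0.1, 0.2, 0.3 and 0.5. These values of s are assumptions, not estimates.

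**5. Workload if two coders replace three.** Extra solo codings each = solo/2 − solo/3.

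- 38 solo: 19.0 − 12.7 = 6.3.
- 30 solo: 15.0 − 10.0 = 5.0.
- 29 solo: 14.5 − 9.7 = 4.8.

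**The case against.** The strongest reply is that absence is being argued from incomplete text. The coding paragraph refers back to section 3b11, hypothesis 3a cites section 3d9, and neither was available; some other pages were also missing. Calling one team member non-blinded may imply that others are blinded. This stands as a limit: the claim is about the supplied plan, and one sentence would settle it if masking is described elsewhere. It does not remove the point, because the role assignments that are visible allow the overlap.

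A second reply is that MPCC scoring may follow a tight manual and that coders may work from transcripts. The recording section sends encounters for transcription, while the Aim 1 text says the MPCC does not need it. What Aim 3 coders use is not settled. The planned reliability checks imply some room for judgement, but how far scores could move is unknown.

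A third reply is that the stakes are modest: "The primary goal of the Aim 3 pilot RCT is to assess the feasibility of PCI". That is correct, and it sets the label.

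Several stronger readings are tempting but unsupported:

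- **The PI will treat and then score a known share of control participants.** The PI is only an example of a control interventionist, and no coding split is given, so any percentage would come from assumptions.
- **The PCI interventionist also codes.** Nothing says so.
- **The interviews unmask coders.** The plan seeks "qualitative feedback from a subsample of pilot RCT intervention arm participants", but it does not say that interviewers code. Interviews follow the third time point, whereas the MPCC is assessed at the second.
- **The name-to-ID link file or the arm-specific utilization form reveals arm to coders.** The link file is not said to hold allocation, and coders are not said to handle the form.

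**Conclusion.** The point holds in limited form. As supplied, the plan permits a person who delivered or supervised sessions to score the 3b(1) outcome for those same participants, and no stated safeguard prevents arm-aware scoring. This is more than a missing detail, because the plan itself names the PI as coder and as a possible non-blinded control interventionist.

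The size of any bias is not derivable. Exposure could be nil if no coder delivers or supervises sessions. The feasibility results and the self-reported functioning outcomes in 3b(2) do not depend on these coders and are unaffected. The conclusion assumes that the unavailable sections do not already provide masking. It is a cheap improvement and does not threaten the pilot's main purpose.

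**What to change.** Add to the Appointment recording coding paragraph:

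1. MPCC coders are not given allocation, and receive recordings in random order under a code not linked to arm.
2. No one codes, alone or jointly, a recording of a participant whose sessions they delivered or supervised.
3. A coder who treated or supervised most of one arm codes neither arm's recordings; otherwise coder and arm would be confounded. For example, the PI limits their coding role to training coders on Aim 1 recordings, which have no arms, or does not deliver or supervise sessions.
4. The report states which coders knew the arm.

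Apply this to recordings not yet coded, since the payment and consent sections show that Aim 3 enrolment had begun.

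**Cost.** Sample size and analysis model are unchanged. Some roles must be reassigned, and someone must track who treated or supervised whom. If the PI stops coding, each of two remaining coders takes about 5 to 6 more solo recordings (38 to 48 recordings, equal split), and the agreement check becomes two-way. If a second coder also delivers many sessions, only one coder might remain, so control delivery should be assigned with this in mind. Masking will be imperfect, because appointment content may reveal the arm and some staff may already know it.
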